Study Population and Eligibility. We will create a retrospective cohort of RWPA clients exposed to the D2S intervention. Eligible clients include those exposed at early implementation sites in Period 1 (about half of the clients entering the trial in Period 1) and at all 27 sites in Period 2 (all clients entering the trial in Period 2), for a projected N≈700, using available (July 2017 through December 2019) data from the originally expected 26 sites.

Analysis Plan. Statistical analyses for Aim 2 will include data exploration via bivariate analyses and descriptive statistics to assess required statistical modeling assumptions. We will identify modifiable factors for TVS among

eligible clients on each D2S report at implementing sites. For these analyses, we will use logistic regression to calculate unadjusted and adjusted odds ratios (ORs of TVS), with generalized estimating equations to account for clustering within RWPA agencies. Multivariate models will be adjusted for non-modifiable yet confounding characteristics including demographics (e.g., sex, age, income, education) and Period (1 or 2) to account for temporal trends. We will separately and jointly map variables to the CFIR to understand the independent and combined VS effects of inner and outer setting constructs, thus informing refinements to D2S features. Aim 2 analyses will be conducted via R and SAS software. Hypothesis tests will use a two-tailed, 0.05 significance level. Statistical analyses will be guided by the CFIR and directed acyclic graphs (DAGs) based on our hypotheses, published RCTs, and other literature on potential mediators or confounders of exposure-outcome relationships, which may require more than one model, given DAG specifications regarding causal relationships. Missing data: In our experience with eSHARE and the HIV Registry, missingness for most exposures and confounders of interest is <5%, in which case we will assign the most common value. For missingness $\geq 5\%$, we will employ multiple imputation along with sensitivity assessment of the inferences under varying conditions. Though we believe the missing-at-random assumption to be reasonable for many variables in the merged dataset, we will assess this by chi-square test of association between missingness of each exposure or confounder with the outcome.

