Power Analyses. Among 700 clients exposed to D2S in the trial, using an estimate of an exposure of interest, E, with frequency >5%, we estimate we will have 80% power to detect an AOR of ≥ 1.65 . For higher-level (e.g., site) factors, assuming the original 26 RWPA sites and using a 2019 estimate of the median caseload as 32.5 (IQR: 32, Q1: 20, Q3: 52) and a conservative estimate of the Intraclass Correlation Coefficient (ICC) as 0.1, we estimate 80% power to detect an AOR ≥ 2.3 as statistically significant, at exposure frequencies of 20%-80%.

AIM 3.

Overview. We will gather data on participant views of D2S and preferred D2S intervention features, to inform future refinements, in eight (client and provider) focus groups and in a DCE with RWPA site staff (n=200).

We will convene RWPA client and staff focus groups with D2S implementing agencies to gather data on perceived acceptability and particular aspects of the D2S intervention seen as most relevant to participants, most potentially burdensome (staff) or intrusive (clients), most valuable for enhancing capacity (staff) or existing services (clients), and/or most effective at increasing client treatment engagement. This qualitative work will inform selection of attributes and choice levels for the DCE to ensure robust results. To further inform future delivery of D2S, in Years 3-4 we will conduct the DCE with staff (N=200) at all 27 D2S trial sites.

Focus Group Study Population. We will conduct a total of eight focus groups (three client groups and five staff groups). This number of focus groups was selected to represent the range of relevant variation in terms of program setting and provider role (staff) and intervention experience (clients). Thus, two client groups will be divided by trial outcome (TVS/no TVS), and a third group will engage Spanish-speaking clients involved in the trial regardless of TVS status. Staff groups will be divided by setting (clinical versus non-clinical) and split within setting by program role: administrative, direct support services delivery, or medical care delivery (at clinical sites only – which is why we plan five versus six staff groups). To cushion against the likelihood of some prospective participants failing to show up for the group at

the appointed time and place, we will register up to 12 participants for each group and will expect approximately nine to participate (based on prior experience with similar focus group sessions).

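### Aim 2 fills variables with under 5% missing with their most common value, which biases odds ratios and inflates type I error when missingness differs by TVS; the already planned multiple imputation should cover them

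*Combined protocol and SAP*

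**What the plan says.** Section K, Aim 2, Analysis Plan (Missing data) sets a two-tier rule. On the investigators' experience with the two data systems, most variables are expected to have under 5% missing, "in which case we will assign the most common value". At 5% or more, "we will employ multiple imputation along with sensitivity assessment of the inferences under varying conditions". The plan regards missing at random (MAR) as reasonable for many variables and adds that "we will assess this by chi-square test of association between missingness of each exposure or confounder with the outcome". It does not say what follows if that test is positive, and the test does not alter the rule below 5%.

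The analysis is logistic regression for TVS with generalized estimating equations for agency. "Hypothesis tests will use a two-tailed, 0.05 significance level". The Aim 2 Power Analyses start from "Among 700 clients exposed to D2S in the trial" and claim 80% power for an adjusted OR of 1.65 or more. No other section changes the missing-data rule.

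**The concern.** Because most variables are expected to fall below 5%, modal fill is the default and multiple imputation the exception. For a binary exposure present in fewer than half of clients, the most common value is unexposed. Every exposed client with a missing value is therefore counted as unexposed. If clients without TVS have more missing values, the fill removes proportionally more non-TVS clients from the exposed group, and an association appears where none exists.

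This pattern is plausible, though that is a judgement. The Aim 2 Overview says that substance use and housing stability are assessed semi-annually by the programs, and clients who miss assessments may also be less likely to reach suppression. Aim 2 exists to find modifiable determinants of TVS and to guide changes to D2S, so a distorted odds ratio bears directly on its purpose. The 5% switch also gives a variable with 4.9% missing a weaker method than one with 5.1%.

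**Working it through.** **Inputs from the documents.** N=700 and a target OR of 1.65 (Aim 2 Power Analyses); two-sided 0.05 (Aim 2 Analysis Plan); TVS of 43.7% without D2S and 59.1% as the detectable rate with D2S (Aim 1 power section).

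**Assumptions.** TVS of 55% in the unexposed, which lies between those two rates; one binary exposure with frequency f of 10%, 25% or 40%; missingness m1 in TVS and m0 in non-TVS; unadjusted 2x2 analysis; no clustering. The documents give no value for m1 or m0.

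**The plan's own figure.** The plan gives no figure for the effect of modal fill. Its 80% power at 1.65 is roughly matched only at exposure frequencies of about 23-28%; full-data power here is 79% at f=25%. At 5% exposure it is 25-31%. That is a separate matter.

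**Null case, large sample.** After modal fill,

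OR* = [(1-m1)(1-f+f·m0)] / [(1-m0)(1-f+f·m1)].

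For m0=0.09, m1=0.01, f=0.25: (0.99 × 0.7725)/(0.91 × 0.7525) = 0.7648/0.6848 = 1.117. Overall missingness is 0.55 × 1% + 0.45 × 9% = 4.6%, just under the threshold.

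**Null case, simulated at N=700.** Only data sets with observed missingness under 5% are kept, since otherwise the plan would switch to multiple imputation. Entries are mean OR and type I error.

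| Missing, non-TVS / TVS | f=10% | f=25% | f=40% |
|---|---|---|---|
| 9% / 1% | 1.09, 6% | 1.11, 8% | 1.13, 12% |
| 7% / 3% | 1.05, 5% | 1.05, 6% | 1.06, 7% |
| 3.9% / 0.4% (2% overall) | 1.04, 5% | 1.05, 6% | 1.06, 6.6% |
| 4.8% / 4.8% | 1.00, 5% | 1.00, 5% | 1.00, 5% |

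For the third row, m1 = 0.02/(0.55 + 0.45 × 9) = 0.0043 and m0 = 9 × m1 = 0.039. Without the restriction, the first row is 1.10, 1.12 and 1.15, with type I error of 6%, 9% and 14%.

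**Direction at a true effect (9% / 1%, all data sets).** With true OR 1.65 and f=0.25, TVS in the exposed is 2.0167/3.0167 = 0.6685, and

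OR* = [0.6685 × 0.99 × (0.75 × 0.45 + 0.25 × 0.3315 × 0.09)] / [0.3315 × 0.91 × (0.75 × 0.55 + 0.25 × 0.6685 × 0.01)] = 1.83.

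The simulated range is 1.83-1.86, and rejection rises: 91% against 79% with full data at f=25%, and 97% against 88% at f=40%. With true OR 1/1.65 = 0.61 the estimate moves towards 1 (0.68 at f=25%, 0.71 at f=40%). Power falls to about 57% against 81-82% with full data at f=25%, and to 60% against 90% at f=40%. Keeping only data sets under 5% missing, those two powers are about 60% and 66%.

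**Interval width.** Under 9% / 1% at f=25% and the null, the mean standard error and the empirical spread are both 0.180. With equal missingness, coverage is 95%.

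**At the plan's 43.7% TVS.** With 7.5% / 1% and f=40%, modal fill gives a null OR of 1.12 and type I error of 11%. Multiple imputation with TVS in the model gives 1.005 and 4.3%. At true OR 1.65, modal fill gives 1.83 with 90% coverage and multiple imputation 1.66 with 94%. With more missing in TVS the bias reverses: 10% in TVS and 0% in non-TVS gives a null OR of 0.84-0.89.

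**The chi-square.** TVS is the outcome variable itself. Missingness that depends on an observed outcome is compatible with MAR, and a lack of association does not show that missingness is unrelated to the unseen value. The test would flag 6.5% / 2% about 85% of the time and 7.5% / 1% more than 99% of the time, yet the plan would still apply modal fill.

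**The case against.** The strongest reply is that the harm needs a split that the documents do not report. Trial clients are actively enrolled and in care (Section E), so a ninefold difference in missingness needs justification. Under 5% may also mean well under 5%: at about 2% overall, even a 9:1 split leaves type I error at about 5% to 6.6%. With equal missingness there is no null bias, and an effect of 1.65 is attenuated by at most about 2%. Aim 2 is secondary and observational, and the chi-square would usually reveal the damaging pattern. All of this stands and limits the size of the point. It does not defend the rule, because no action follows a positive chi-square and modal fill has no compensating statistical advantage.

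A reader might infer two stronger harms. One is that modal fill costs power at the plan's target OR of 1.65. Under more missingness in non-TVS the opposite holds: that effect is overstated and rejected more often, and power is lost for effects below 1. The other is that treating filled values as observed makes intervals materially too narrow. The standard errors match the empirical spread; coverage falls because the estimate shifts.

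**Conclusion.** The point holds in conditional form. When missingness differs by TVS, modal fill biases Aim 2 odds ratios and raises type I error: about 1.09-1.13 and 6-12% under a strong assumed split near the 5% ceiling, and about 1.04-1.06 and 5-7% under milder ones. If non-TVS clients have more missing values, exposures that raise TVS are exaggerated and barriers to TVS are understated. The reverse split, or an exposure present in more than half of clients, flips the sign.

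These sizes rest on assumed splits and an unadjusted model without clustering; filled confounders were not simulated. The documents do not support a claim that the bias will occur or that it is large, and the primary Aim 1 test does not use this rule. It is a change that should be made because it is cheap and the better method is already in the plan.

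**What to change.** Delete the modal-value rule. Apply the planned multiple imputation to every incomplete Aim 2 exposure and confounder, whatever its percentage missing, with TVS, period and agency in the imputation model. Report the chi-square of missingness against TVS descriptively, as a description of where data are missing, and stop presenting it as an assessment of MAR. Keep the planned sensitivity assessment, extended to all imputed variables, since multiple imputation does not protect against missingness that depends on the unseen value itself.

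The cost is a few lines of SAP wording and a little more computing. The imputation code is already needed for any variable at 5% or more, and no new data are required.

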Power Analyses for the Trial. Our power analyses are based on simulated D2S reports on earlier time periods, generated using available and complete merged surveillance and program data (through 2019 for D2S reports and through September 2020 for six-month follow-up, where follow-up begins two months following the end of a given report year). For the 26 sites and 48 programs originally expected to be included in the trial based on preliminary data, six rounds of baseline reports (on July 2016-June 2017, calendar year [CY] 2017, July 2017-June 2018, CY2018, July 2018-June 2019, and CY2019) list 1,283 unique clients who would be eligible for the trial if we imagine that trial as having a Period 0 starting in September 2017. When we allow clients to count in multiple periods, the 1,283 account for 1,782 potential trial outcomes; at baseline, ~43.7% of those outcomes are TVS (VS in a six-month period starting two months after the end of the report year in which clients were unsuppressed). Based on simulation studies using a mock pairing of sites and repeated randomization of sites within matched pairs, we estimate 80% power to detect an OR of 1.86 (RR of 1.35), corresponding to 59.1% achieving TVS with D2S, versus the base rate (43.7%). Due to the smaller N when we omit repeat observations, the sensitivity analysis will have lower statistical power than the primary analysis; however, preliminary calculations indicate that an OR ~2.08 (RR ~1.41) will be detectable. For the secondary endpoint, time to VS (with 12 months of follow-up), we will use Cox regression based on a model analogous to that used for TVS. Insofar as there will be more events for the secondary outcome than for TVS, and insofar as time-to-event analyses can be more powerful than binary outcome analyses, we expect power >80% to detect a doubling of the hazard ratio for the intervention versus control condition.

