Qualitative Analysis. Interviews will be audio-recorded and transcribed. Thematic analysis will be conducted in Dedoose using a ‘framework fit’ technique, applying pre-defined codes derived from CFIR and RE-AIM. We will also use grounded exploration to interpret categories’ meaning and attend to emergent themes salient to participants. This combined inductive-deductive approach suits the structured nature (well-defined domains) of the implementation science (IS) frameworks being applied. Initial codes will be identified by independent review of three transcripts by two study team members in dialogue with the senior qualitative methods advisor. The draft codebook will then be independently applied to a single transcript, with discrepancies resolved in consensus sessions to optimize inter-rater reliability, yielding a final codebook to be applied to the entire dataset. Also in this phase, we will use process analysis to map implementation trajectories by program as a means of comparing programs’ intervention uses, which may be associated with programs’ better or worse outcomes. Qualitative and quantitative analyses will be integrated by examining thematic patterns reflecting RE-AIM and CFIR implementation constructs as they explain client and organizational outcomes across programs. Aim 1 qualitative and quantitative phases will proceed concurrently, with the qualitative analysis serving a primarily explanatory function in relation to quantitative findings, while also having direct applications in terms of informing future refinements to the D2S intervention to optimize implementation and sustainability.

AIM 2.

Overview. We will create a retrospective, unduplicated cohort of unsuppressed clients exposed to the D2S condition in order to identify modifiable determinants of D2S response. VS outcome data for Aims 1 and 2 will be derived from the Registry. Client-level DOHMH-funded program reporting will supply measures of potential VS determinants, including modifiable factors such as substance use and housing stability – assessed semi-annually in RWPA. Organizational factors will be pulled from agency contract documents.

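### The Aim 2 client-level power statement pairs an AOR of 1.65 with exposure frequencies above 5%, but 700 clients give 80% power at 1.65 only for exposures held by roughly 25–75% of them

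*Combined protocol and SAP*

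**What the plan says.** Section K, Aim 2, Power Analyses, gives one power statement for client-level factors. It begins "Among 700 clients exposed to D2S in the trial" and continues, for an exposure "with frequency >5%, we estimate we will have 80% power to detect an AOR of ≥ 1.65". The paragraph states no TVS rate, covariate correlation or design effect for such factors. Its next sentence covers site-level factors separately, with an ICC of 0.1 and a stated exposure range of 20–80%.

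The Aim 2 Analysis Plan supplies the test level: "Hypothesis tests will use a two-tailed, 0.05 significance level". The model is logistic regression "with generalized estimating equations to account for clustering within RWPA agencies", with adjusted as well as unadjusted odds ratios. The Aim 2 Overview fixes the unit of analysis: "We will create a retrospective, unduplicated cohort of unsuppressed clients exposed to the D2S condition". Each client therefore counts once, and repeat observations add no information.

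**The concern.** A lower bound on exposure frequency reads as the range over which the claim holds, here everything above 5%. In a cohort of fixed size, power for a binary factor depends heavily on how many clients carry it. With 35 exposed and 665 unexposed, the standard error of the log odds ratio is about 0.35. An effect of ln(1.65) = 0.50 is then only about 1.4 standard errors, whereas 80% power at two-sided 0.05 needs about 2.8.

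This is the only client-level power statement for Aim 2, whose purpose is to find modifiable determinants of response. A factor held by 5–10% of clients with a true odds ratio of 1.65 would be missed about half to three-quarters of the time. The plan's sentence implies a miss rate of one in five.

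**Working it through.** **Inputs**
- N = 700, exposure frequency f > 5%, AOR 1.65, power 80%: Aim 2, Power Analyses.
- Two-sided 0.05: Aim 2, Analysis Plan.
- TVS in the unexposed, p0: not given for Aim 2. Assumed range 43.7% to 59.1%, the rates without and with D2S in the Aim 1 section on power for the trial.
- No clustering or covariate penalty. This favours the plan.

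**Quick check on the log scale, f = 5%**

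SE(log OR) ≈ 1/√[N f(1−f) p0(1−p0)] = 1/√[700 × 0.05 × 0.95 × 0.437 × 0.563] = 0.35.

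Required log OR ≈ (1.96 + 0.84) × 0.35 = 0.98, an OR of about 2.7. The plan's value is ln(1.65) = 0.50.

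**Two-proportion calculation, f = 5%**

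n1 = 35, n0 = 665, p1 = 1.65·p0 / (1 − p0 + 1.65·p0), and p̄ is the pooled proportion.

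Power ≈ Φ{[(p1 − p0) − 1.96·SE0]/SE1}, with SE0 = √[p̄(1−p̄)(1/n1 + 1/n0)] and SE1 = √[p1(1−p1)/n1 + p0(1−p0)/n0].

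- p0 = 0.437: p1 = 0.5615, SE0 = 0.0862, SE1 = 0.0861. Φ[(0.1245 − 0.1690)/0.0861] = Φ(−0.52) ≈ 0.30.
- p0 = 0.591: p1 = 0.7045, SE0 = 0.0851, SE1 = 0.0794. Φ[(0.1135 − 0.1668)/0.0794] = Φ(−0.67) ≈ 0.25.

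**Attempts to reproduce the stated 80% at f = 5%**

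| Variant | Power at OR 1.65 |
|---|---|
| Pooled test, p0 43.7–59.1% | 25–30% |
| Wald test on the log OR | 26–30% |
| Simulation, score and likelihood-ratio tests | 25–31% |
| Protective effect, OR 1/1.65 | 26–31% |
| One-sided 0.05 | 37–42% |
| 1,782 outcomes in place of 700 clients | 57–64% |

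None reaches 80%. With p0 varied from 30% to 70%, two-sided power stays at or below about 31%. Reaching 80% at f = 5% would take about 2,630–2,970 clients.

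**By exposure frequency (N = 700, p0 43.7–59.1%)**

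| Exposure | Power at OR 1.65 | OR detectable with 80% power |
|---|---|---|
| 5% | 25–30% | 2.67–3.05 |
| 10% | 45–51% | 2.03–2.16 |
| 20% | 70–75% | 1.70–1.76 |
| 25% | 77–82% | 1.63–1.68 |
| 50% | 88–91% | 1.53–1.56 |
| 75% | 79–82% | 1.63–1.67 |
| 80% | 72–75% | 1.70–1.74 |
| 90% | 50–51% | 2.02–2.09 |

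Power at 1.65 crosses 80% at an exposure of 23% (p0 = 43.7%) or 28% (p0 = 59.1%). It falls back below 80% at about 77% or 74% respectively. A Wald calculation is less favourable at 5% exposure, with a detectable OR of 2.85–3.77.

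**Effect of clustering.** The plan gives no design effect for client-level factors. With an assumed value of 1.5 (effective N = 700/1.5 ≈ 467), power at 1.65 and 5% exposure falls to 18–22%. The detectable OR is then 3.4–4.2 at 5% exposure and about 1.7 at 50%.

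**The case against.** The strongest defence is that the sentence is loosely worded: it says above 5%, not at 5%, and 1.65 is about right for common exposures. That is so. The odds ratio reproduces for exposures of about 23–28% and upward, to about 74–77%, so the fault lies in the frequency bound rather than in 1.65 itself. But as written the sentence covers every frequency above 5%, and it fails from there to about a quarter. If a particular higher frequency was used, it is not stated.

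A second defence is that little depends on the figure. Aim 2 is a secondary, observational analysis of a cohort whose size the trial fixes, and the figure sets no sample size, enrolment target or decision rule. This stands, and it limits the weight of the point.

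Two stronger readings are tempting. A reader might infer that non-significant results for rarer factors will be reported as adequately powered negatives. The documents do not say so: they plan odds ratios guided by an implementation framework and causal diagrams, and never state that a non-significant factor will be declared absent. A reader might also infer that Aim 2 as a whole lacks power. The documents give no exposure prevalences. The modifiable examples named, substance use and housing stability, could well be common among clients of harm reduction, mental health and housing programs. How much of Aim 2 is affected is unknown.

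**Conclusion.** The sentence is wrong as written, with moderate severity. With 700 clients and a two-sided 0.05 test, 80% power at an AOR of 1.65 holds only for exposures held by roughly 25–75% of clients, not for all those above 5%. At the stated bound, power is about 25–30% and the detectable AOR about 2.7–3.0.

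The exact values rest on the borrowed TVS range. The conclusion does not, since no TVS rate tried brings power at 5% exposure above about 31%. Clustering and covariate adjustment were left out, and allowing for them would widen the gap. The point does not touch the primary trial analysis or enrolment, and it does not show that Aim 2 will be misinterpreted or is underpowered throughout.

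**What to change.** Restate the sentence so that an AOR of 1.65 with 80% power applies only to exposure frequencies of about 25–75%. Add best-case detectable AORs by frequency:

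| Exposure frequency | Detectable AOR, best case |
|---|---|
| 5% | about 2.7–3.0 |
| 10% or 90% | about 2.0–2.2 |
| 20% or 80% | about 1.7–1.8 |
| 25% or 75% | about 1.65 |
| 50% | about 1.55 |

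State beside the table the TVS rate assumed (here 43.7–59.1%, from Aim 1) and that no clustering or covariate penalty is included. Say that the values rise once the planned GEE clustering and adjustment are allowed for; an assumed design effect of 1.5, for example, gives about 3.4–4.2 at 5% and about 1.7 at 50%. If the study team has its own design effect for client-level factors, the table should be recalculated with it.

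The cost is one sentence and a small table. The stated power becomes less favourable; design, data and enrolment do not change.

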Viral Suppression Analysis Plan. The analysis plan is based on the exact, conditional distribution theory of non-central multiple hypergeometric distributions and their convolutions, enabling us to estimate the effect of the intervention as a single parameter, while allowing for arbitrary site and period effects within matched pairs. The conventional statistical analysis proposed for cross-sectional stepped-wedge designs (i.e., with independent samples of patients enrolled at each transition step) assumes a mixed model with random cluster effects and fixed period effects, yet this is not appropriate for our matched-pairs stepped-wedge trial, since the matching will be under the investigators’ control and so should be conditioned upon. In addition, the generalized linear mixed model requires an unverifiable assumption of normal distribution for random effects and has poor variance estimation performance in small samples (of clusters), even with robust variance estimation, such that jackknifing must be used. Our exact conditional analysis avoids these problems. We initially assume a random-effects model that accounts for clustering by assuming conditional independence of client responses within clusters (sites matched within pairs). As more fully described below, the random effects allow for arbitrary site-level differences within pairs (assumed constant across periods) and for arbitrary period effects (assumed constant for each site within a pair, though allowed to vary between pairs). Unlike the conventional analysis for cross-sectional stepped-wedge designs, however, our exact conditional approach proceeds from the initial assumptions by removing the random site-difference and period effects entirely from the analysis, ultimately allowing inferences about the intervention to be drawn from a single-parameter conditional distribution.

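### The Aim 2 site-level power claim (80% for AOR 2.3 at 20%-80% exposure) holds only near balanced exposure on the plan's own inputs, and no small-sample variance method is named for agency factors

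*Combined protocol and SAP*

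**What the plan says.** Section K, Aim 2, Power Analyses, covers factors that vary between sites rather than between clients. It works by "assuming the original 26 RWPA sites". Clustering enters through a "conservative estimate of the Intraclass Correlation Coefficient (ICC) as 0.1", and cluster size through a "2019 estimate of the median caseload as 32.5 (IQR: 32, Q1: 20, Q3: 52". From these it concludes: "we estimate 80% power to detect an AOR ≥ 2.3 as statistically significant, at exposure frequencies of 20%-80" percent. It gives no formula, no TVS rate and no scale for the ICC.

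The Aim 2 Analysis Plan fits logistic regression "with generalized estimating equations to account for clustering within RWPA agencies" and adds: "Hypothesis tests will use a two-tailed, 0.05 significance level". It names R and SAS, but no working correlation, variance estimator, small-sample correction or reference distribution. The Aim 2 cohort is projected at about 700 clients, and 27 agencies now take part.

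In the Aim 1 Viral Suppression Analysis Plan, the sponsor argues against the generalized linear mixed model partly because it "has poor variance estimation performance in small samples (of clusters), even with robust variance estimation, such that jackknifing must be used".

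**The concern.** A site-level factor is shared by everyone at an agency, so the information on it is limited by the number of agencies and by how evenly they split on the factor. A single detectable AOR for all exposures from 20% to 80% is therefore suspect: with 26 sites, 20% exposure means about 5 sites against 21.

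Aim 2 maps inner- and outer-setting factors to CFIR in order to guide refinement of D2S. If the power statement is too generous at the ends of its range, a null result for an uncommon agency feature will be read as more informative than it is. If the test for such a feature is also run with a default robust variance, some positive results will be less reliable than their P-values suggest.

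**Working it through.** **Inputs.** From Aim 2, Power Analyses: 26 sites, caseload 32.5, ICC 0.1, AOR 2.3, exposure 20%-80%. From the Aim 2 Analysis Plan: two-sided 0.05. The TVS rate in the unexposed group is an assumption. Power Analyses for the Trial (Aim 1) gives 43.7% without D2S and 59.1% with it, and both are used below. Every Aim 2 client is D2S-exposed, so 59.1% is arguably the closer of the two.

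**Step 1: effective sample size.** Design effect = 1 + (32.5 − 1) × 0.1 = 4.15. Clients = 26 × 32.5 = 845. Effective N = 845 / 4.15 = 203.6.

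**Step 2: power.** The check is a two-proportion comparison with pooled variance under the null, with effective N split by exposure share. For exposed TVS p1 and unexposed TVS p0, p1 = 2.3·p0 / (1 − p0 + 2.3·p0).

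Example at 20% exposure and p0 = 0.437:
- p1 = 1.0051 / 1.5681 = 0.641, so the difference is 0.204.
- Effective group sizes are 162.9 and 40.7, and the pooled proportion is 0.478.
- The standard error is 0.0875 under the null and 0.0846 under the alternative.
- Power = Φ[(0.204 − 1.96 × 0.0875) / 0.0846] = Φ(0.38) = 65%.

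| Exposure | Power at 2.3, p0 43.7% | Detectable AOR | Power at 2.3, p0 59.1% | Detectable AOR |
|---|---|---|---|---|
| 20% | 65% | 2.72 | 56% | 3.08 |
| 30% | 77% | 2.38 | 69% | 2.60 |
| 35% | 80% | 2.30 | 73% | 2.49 |
| 50% | 84% | 2.21 | 78% | 2.35 |
| 65% | 80% | 2.29 | 75% | 2.44 |
| 70% | 77% | 2.37 | 72% | 2.53 |
| 80% | 66% | 2.68 | 62% | 2.89 |

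The plan's figure is reproduced near balanced exposure with p0 = 43.7%, and not at the ends.

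**Step 3: can another input rescue the ends?**
- *TVS rate.* Over all base rates scanned, power at 20% or 80% exposure never exceeds 66%.
- *Caseload.* With 26 sites and a proportion-scale ICC of 0.1, effective N cannot exceed 26 / 0.1 = 260. Power at the ends is then at most 76.5%. About 284-288 would be needed at p0 = 43.7%.
- *One-sided test.* At most 77% with the stated caseload, and the plan specifies two-sided tests.
- *ICC scale.* A latent-scale ICC of 0.1 is a logit variance of (π²/3) × 0.1/0.9 = 0.366, or about 0.077 on the proportion scale. Design effect = 1 + 31.5 × 0.077 = 3.43 and effective N = 845 / 3.43, about 247. Power at the ends is 73%-74% (p0 43.7%) or 65%-70% (p0 59.1%). The limit of 260 does not apply on this reading.

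**Step 4: restated figure for about 700 clients at 27 agencies, ICC 0.1 on the proportion scale.**
- *Equal sizes.* Mean size is 700 / 27 = 25.9 and effective N = 700 / (1 + 24.9 × 0.1), about 200. The detectable AOR is 2.22-2.37 at 50% exposure and 2.70-3.12 at 20% or 80%.
- *Unequal sizes.* Lognormal caseloads with the spread implied by the quoted quartiles have σ = ln(52/20) / (2 × 0.674), about 0.71. Under an exchangeable model, effective N is the sum over agencies of m_i / (1 + (m_i − 1) × 0.1), about 183. The detectable AOR is 2.31-2.48 at 50% and 2.83-3.32 at 20% or 80%.

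Together: about 2.2-2.5 at 50% exposure and about 2.7-3.3 at the ends.

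**Step 5: type I error without a small-sample correction.** One simulation used 27 agencies, 700 clients, ICC 0.1, TVS 59.1%, unequal sizes (assumed CV 0.65), exchangeable GEE with client covariates, and the default sandwich with a z test. It gave 12.6% with 5 agencies exposed, 12.2% with 22, 8.0% with 8 and 7.1% with 13, from about 2,400-2,900 replicates each (Monte Carlo SE 0.5-0.7 points). Across all settings tried, the ranges were 10%-14% near a 20/80 split, 8%-10% with 8 agencies and 7%-9% when balanced. A Mancl-DeRouen correction with a t reference gave 5%-7% with 5 or 21 exposed.

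**The case against.** **The plan is right for balanced factors.** This stands in part: with p0 = 43.7%, AOR 2.3 is detectable at about 35%-65% exposure. A reader might infer that site-level inference in Aim 2 fails altogether, but the calculation does not show that.

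**The TVS rate and ICC scale are not given, so any recalculation rests on assumptions.** True. The ICC scale matters: on the latent reading with p0 = 43.7%, power is about 84% already at 30% and 70% exposure. But power at 20% and 80% stays below 80% on either reading.

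**845 clients against a cohort of 700 is not a contradiction.** This stands. The 32.5 is a 2019 median, and a median times the number of sites is not a cohort total. With 26 equal sites, moving from 845 to 700 changes the detectable AOR at 20% exposure only from 2.72 to 2.78 (p0 43.7%).

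**Unequal caseloads.** The quartiles might suggest a detectable AOR of 3.4-3.8 at the ends. That comes from a size-weighted design effect, 1 + ((1 + CV²)m − 1) × ICC, which gives an effective N of about 136. It does not describe an exchangeable GEE, where effective N is about 183. The plan commits to neither, so 3.4-3.8 should not go into it.

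**The plan never says it will use an uncorrected sandwich.** Correct. The Aim 2 text is silent, and the jackknife remark concerns the mixed model in Aim 1. A reader might infer that Aim 2 will flag too many false site factors, or that the error rate doubles to triples generally. The documents support only a request to specify the method, and inflation of that size is confined to splits near 20/80.

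**Aim 2 is a secondary observational analysis.** Also true: refinements of D2S draw on findings from all Aims, so site factors alone do not determine them.

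**Conclusion.** The stated 80% power for AOR 2.3 does not follow from the plan's inputs at the ends of its exposure range. With equal caseloads and a proportion-scale ICC, power at 20% or 80% exposure is about 56%-66% for TVS of 59.1%-43.7%, and no TVS rate or caseload brings it to 80%. On a latent-scale ICC it is about 65%-74%. Near balance the figure is met at TVS 43.7% and narrowly missed at 59.1%. These are normal-approximation results with no allowance for covariate adjustment or a t reference, so they favour the plan.

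The variance point is secondary and conditional. It is an omission in the Aim 2 Analysis Plan that matters most for agency factors split near 20/80, and only if the default uncorrected sandwich is used.

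**What to change.** **(a) Aim 2, Power Analyses.** Replace the single figure with a detectable AOR by exposure frequency for about 700 clients: about 2.2-2.5 at 50% exposure and about 2.7-3.3 at 20% or 80%. State beside it the assumed TVS rate (here 43.7%-59.1%), the ICC scale, the caseload spread and the working correlation.

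**(b) Aim 2, Analysis Plan.** For agency-level factors, specify a Mancl-DeRouen or jackknife GEE covariance with a t reference on agencies minus site-level parameters (27 − 2 = 25 for one factor plus an intercept).

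**Cost.** One restated figure and one sentence, with no change to design or data. Intervals for site factors will be wider and the stated power lower. In simulation, the Mancl-DeRouen correction with a t reference left about 41%-53% power for OR 2.3 when 5 or 21 of 26 sites carried the factor, so null results for such factors should be reported as inconclusive.
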